8.6.5. Time Period and Frequency for Collecting AE and SAE Information

AEs and SAEs will be monitored for and collected at the time points specified in Schedule of Events and Procedures ([Table 3](#)), from the signing of the ICF until the subject withdrawal or the scheduled exit visit. (Note: Although AEs will be monitored for and collected prior to study medication administration, the statistical data analysis will determine and summarize treatment-emergent AEs, i.e., those AEs that began or worsened in severity after the first study medication administration.)

All SAEs will be recorded and reported to Santen or designee immediately and under no circumstance should this exceed 24 hours, as indicated in [Section 12.4](#), Appendix D. The investigator will submit any updated SAE data to Santen within 24 hours of it being available.

Investigators are not obligated to monitor for new AEs or SAEs after conclusion of the study participation. However, if the investigator learns of any SAE, including a death, at any time after a subject has been discharged from the study, and he/she considers the event to be reasonably related to the study medication or study participation, the investigator must promptly notify Santen.

8.6.6. Method of Detecting AEs and SAEs

The method of recording, evaluating, and assessing causality of AEs and SAEs and the procedures for completing and transmitting SAE reports are provided in [Section 12.4](#), Appendix D. During the double-masked period, regardless of the source of the reported occurrence of an AE in a subject, the masked investigator will assess the causality of the AE.

Care will be taken not to introduce bias when detecting AEs and/or SAEs. Open-ended and non-leading verbal questioning of the subject is the preferred method to inquire about AE occurrences.

8.6.7. Follow-up of Adverse Events

All reported AEs (related and unrelated) should be followed until resolution or until the subject's participation in the study ends. Subjects with the following types of events should be followed by the Investigator until the event is determined to be resolved, irreversible, chronic, stable, the subject withdraws consent, or no further information can be reasonably obtained.

Independent of whether a subject has already had their scheduled study exit visit or not, any ongoing following types of event should be followed by the investigator until the event is determined to be resolved, irreversible, stable, the subject withdraws consent, or no further information is available.

- On-going SAEs
- On-going ESIs, including pregnancy and medication errors resulting in AE's
- Early termination and withdrawal from the study due to study medication related AEs
- The other types of related AEs should be also followed by the same manner as SAEs in principle, and this follow up should be continued, as needed, up until the time database lock. Generally, the status/resolution of the AE should be confirmed via an on-site visit, frequency as per investigator's judgement. However, in cases where the investigator considers an on-site visit is not necessary, such as with an AE based on subjective symptoms, the Investigator may confirm the outcome of the AE by telephone, email, etc.
- The other types of unrelated AE should be followed until resolution or the scheduled exit visit

If the information requested by Santen is not part of the eCRF, or when database lock has already been completed, the site's response to follow-up requests should be emailed, faxed, or reported in writing to Santen Global Pharmacovigilance of Emergency Contact Information.

In addition, on a case by case basis, Santen (or designee) may request follow up beyond the scheduled exit visit.

The follow-up information on an individual SAE or AE (or ESI) will be entered into the eCRF prior to database lock. If the information requested by Santen is not part of the eCRF, or when database lock has already been completed, the site's response to follow-up requests should be emailed to [contact] or reported in writing and fax to [contact] (in the US).

8.6.8. Manual Back-Up Reporting Procedures

This study is utilizing an EDC system for data entry. In the event that the EDC system is unavailable for electronic reporting, the manual back-up reporting procedures below should be followed.

- Complete an AE Form, SAE Form, Pregnancy Form, Medication Error Form, or ESI Form as appropriate.
- Attach a cover sheet with your contact information and address to Santen (or its designee) ([Table 1](#)).
- Email (preferred) or Fax the cover sheet and the completed form(s) to Santen (or its designee) ([Table 1](#)) at ‘[contact]’ or [contact] (in the US).

When the EDC system becomes available, the EDC system should be updated with all previously reported information.

8.6.9. Regulatory Reporting Requirements for SAEs

Prompt notification by the investigator to Santen of an SAE is essential so that legal obligations and ethical responsibilities towards the safety of subjects and the safety of a study intervention under clinical investigation are met.

Santen has a legal responsibility to notify both the local regulatory authority and other regulatory agencies about the safety of a study intervention under clinical investigation. Santen will comply with country-specific regulatory requirements relating to safety reporting to the regulatory authority, IRB/IEC, and investigators.

Santen will prepare investigator safety reports for suspected unexpected serious adverse reactions (SUSAR) according to local regulatory requirements and Santen policy and forward them to investigators as necessary. An investigator who receives an investigator safety report describing an SAE or other specific safety information (e.g., summary or listing of SAEs) from Santen will review and then file it along with the Investigational Brochure and will notify the IRB/IEC, if appropriate according to local requirements.

9. STATISTICAL CONSIDERATIONS

This section outlines topics related to the statistical methods used in the design and analysis of the study. A more detailed description of all the analyses and methods is provided in the SAP.

9.1. Interim Analysis

There is no planned interim analysis for this study.

9.2. Final Analysis

An unmasked final analysis will be performed after all subjects completed Month 3 or discontinued prematurely. The analysis will evaluate the efficacy and safety of DE-126 Ophthalmic Solution 0.002% once daily compared with Timolol Maleate Ophthalmic Solution 0.5% twice daily.

9.3. General Considerations

Descriptive statistics, unless otherwise noted, will include the number of subjects (N), mean, SD, median, minimum, and maximum for continuous variables and N and percent for categorical variables.

The study eye will be defined as the eye that qualifies per inclusion criteria at Visit 2 (Baseline, Day 1). For example, IOP must be ≥ 22 mmHg at all IOP measurement time-points (08:00, 10:00, and 16:00). See [Section 5.1](#) and [Section 5.2](#) for all inclusion/exclusion criteria. If both eyes qualify, the eye with the higher mean diurnal IOP at Visit 2 (Baseline, Day 1) will be the study eye. If both eyes have the same mean diurnal IOP at baseline, then the right eye will be designated as the study eye.

Additional considerations will be described in SAP which will be finalized prior to unmasking the data.

9.3.1. Sample Size

The sample size calculation was based on a two-sided Type I error rate of 5% and a non-inferiority margin of 1.5 mmHg. Assuming a between-treatment difference of 0 mmHg, SD of 4.0 mmHg and a correlation coefficient of 0.6 among repeated measures, approximately 280 adult subjects in total (140 subjects per treatment arm) will provide 70% power to demonstrate non-inferiority of DE-126 Ophthalmic Solution 0.002% to Timolol maleate ophthalmic solution 0.5%. Assuming a drop-out rate of 5%, the final needed sample size will be 294 in total, i.e. 147 subjects/arm.

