The sample size calculation is based on a two-sided Type I error rate of 5% and a non-inferiority margin of 1.5 mmHg. Assuming a between-treatment difference of 0 mmHg, a standard deviation (SD) of 4.0 mmHg, and a correlation coefficient of 0.6 among repeated measures, approximately 280 adult subjects in total (140 subjects per treatment arm) will provide 70% power to demonstrate non-inferiority of DE-126 0.002% to Timolol 0.5%.

Assuming a drop-out rate of 5%, the final needed sample size will be 294 in total, i.e. 147 subjects/arm.

For the primary efficacy endpoint, a mixed-effects model for repeated measures (MMRM) will be fitted and 95% confidence interval for least square mean difference in IOP in the study eye between the DE-126/Vehicle arm and the Timolol Maleate arm at each scheduled time point of each post-baseline visit up to Month 3 will be estimated. Non-inferiority is achieved if the upper limit of the two-sided

95% confidence interval for the difference in the mean IOP (DE-126 0.002% - Timolol Maleate 0.5%) is ≤ 1.5 mmHg at all nine time points and ≤ 1.0 mmHg in majority (5 or more) of the 9 time points. If non-inferiority is achieved for the primary endpoint, superiority will be tested.

For the key secondary efficacy endpoint, a MMRM will be fitted on observed cases up to Month 3 on the mean diurnal IOP in the study eye. The least square mean diurnal IOP of each treatment arm and 95% confidence interval for the difference between DE-126/Vehicle and Timolol at Month 3 will be estimated. If

non-inferiority in the primary endpoint is achieved, then the key secondary endpoint will be tested at the 0.05 significance level (2-sided). Non-inferiority is achieved if the upper limit of the two-sided 95% confidence interval for the difference in the mean diurnal IOP (0.002% DE-126 - Timolol Maleate) at Month 3 is ≤ 1.5 mmHg. If non-inferiority is achieved for the key secondary endpoint, superiority will be tested.

All safety outcome measures will be summarized descriptively. Incidences of AEs will be tabulated by the system organ classes and preferred terms specified in the Medical Dictionary for Regulatory Activities ([MedDRA](#)). Separate summaries will be provided for ocular and non-ocular AEs.

TABLE OF CONTENTS

1.	PROTOCOL SUMMARY.....	4
1.1.	Synopsis.....	4
2.	INTRODUCTION	18
2.1.	Study Rationale.....	18
2.2.	Background.....	18
2.3.	Benefit/Risk Assessment	20
3.	STUDY OBJECTIVES AND PURPOSE	22
3.1.	Primary Objective.....	22

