9.3.2. Statistical Hypotheses and Level of Significance

The primary efficacy endpoint is the IOP in the study eye measured at the specified time points: 08:00, 10:00, and 16:00 at Week 2, Week 6, and Month 3 visits.

For the primary endpoint, a MMRM will be used to test the following hypotheses:

$$H_0: \mu_T - \mu_C > \Delta \text{ versus } H_A: \mu_T - \mu_C \leq \Delta$$

Where μ_T and μ_C denote the mean values of the primary endpoint in DE-126/Vehicle arm and Timolol Maleate arm, respectively, and Δ denotes the non-inferiority margin of 1.5 mmHg.

Treatment difference between the DE-126/Vehicle arm and Timolol Maleate arm at each specified time point of each post-baseline visit up to Month 3 will be reported along with 95% confidence intervals. Non-inferiority is established if the upper limit of the two-sided 95% confidence interval for the difference in the mean IOP (DE-126/Vehicle - Timolol Maleate) is ≤ 1.5 mmHg at all nine time points and ≤ 1.0 mmHg in majority (5 or more) of the time points. If the upper limit of the 95% confidence interval for the difference is < 0 at all nine time points, superiority of DE-126 ophthalmic solution 0.002% to Timolol maleate ophthalmic solution 0.5% will be claimed for the primary endpoint.

If non-inferiority in the primary endpoint is achieved, then the key secondary endpoint will be tested: Mean diurnal IOP in the study eye at Month 3.

The corresponding hypothesis is:

$$H_{0S}: \mu_{Ts} - \mu_{Cs} > \Delta \text{ versus } H_{AS}: \mu_{Ts} - \mu_{Cs} \leq \Delta$$

Where μ_{Ts} and μ_{Cs} denote the mean diurnal IOP at Month 3 in DE-126/Vehicle arm and Timolol Maleate arm, respectively; and Δ denotes the non-inferiority margin of 1.5 mmHg.

Non-inferiority is established if the upper limit of the two-sided 95% confidence interval for the difference between DE-126/Vehicle arm and Timolol Maleate arm (DE-126/Vehicle – Timolol Maleate) in the mean diurnal IOP at Month 3 is ≤ 1.5 mmHg. If the upper limit of the 95% confidence interval for the difference is < 0 mmHg, superiority of DE-126 ophthalmic solution 0.002% to Timolol maleate ophthalmic solution 0.5% for the key secondary endpoint will be claimed.

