3.3. Sample Size Planning

The sample size calculation was based on a two-sided Type I error rate of 5% and a non-inferiority margin of 1.5 mmHg. Assuming a between-treatment difference of 0 mmHg, SD of 4.0 mmHg and a correlation coefficient of 0.6 among repeated measures, approximately 280 adult subjects in total (140 subjects per treatment arm) will provide 70% power to demonstrate non-inferiority of DE-126 Ophthalmic Solution 0.002% to Timolol maleate ophthalmic solution 0.5%. Assuming a drop-out rate of 5%, the final needed sample size will be 294 in total, i.e. 147 subjects/arm.

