6.1. Adjustments for Covariates

In general, baseline IOP score will be adjusted in the inferential analysis of each IOP endpoint. Detailed information on covariate adjustment is provided in Section 8.1.

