8.1. Analyses of Primary Endpoint and Key Secondary Endpoint

8.1.1. Primary Analysis

8.1.1.1. Primary Endpoint

The primary efficacy endpoint is the IOP in the study eye at each scheduled timepoint (08:00, 10:00, and 16:00) at each of three follow-up visits, Week 2, Week 6, and Month 3. The nine combinations of three scheduled timepoints at each of three visits are referred to subsequently as nine timepoints. For the primary endpoint, the following hypotheses will be tested:

$$H_0: \mu_T - \mu_C > \Delta \text{ for at least one timepoint}$$

versus

$$H_A: \mu_T - \mu_C \leq \Delta \text{ at all nine timepoints}$$

where μ_T and μ_C denote the mean values of the primary endpoint in the DE-126 arm and the Timolol arm, respectively, and Δ denotes the noninferiority margin of 1.5 mmHg.

The primary analysis of the primary efficacy endpoint will be performed using a MMRM based on the FAS. A separate MMRM will be used for IOP at each scheduled timepoint (8:00, 10:00, or 16:00). For each scheduled k th timepoint, the model will include treatment (T_i), analysis visit (V_j), and treatment-by-visit interaction (TV_{ij}) as fixed effects, and the baseline IOP (B_k) as covariates:

$$IOP_{ijkn} = \mu + T_i + V_j + TV_{ij} + B_k + \varepsilon_{ijkn}$$

where μ denotes the overall mean, and ε denotes the random error associated with the individual subject. The above model allows treatment effect and its variability to vary over study visits.

Correlations of IOP measurements within-subject will be modeled using an unstructured covariance matrix. If there are convergence issues, covariance matrix structures other than unstructured will be tried in the following order: (1) heterogeneous Toeplitz (TOEPH), (2) heterogeneous autoregressive of order 1 (ARH(1)), (3) heterogeneous compound symmetry (CSH), and (4) compound symmetry (CS). The first covariance structure that converges will be used as the primary analysis. Least squares mean IOP values for each treatment arm and differences between least squares treatment arm means and associated 95% confidence intervals will be reported for each of the nine timepoints.

For the subjects who receive IOP-lowering rescue therapy, any IOP values collected after the receipt of rescue therapy will be censored (i.e., treated as missing) in the analyses.

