Noninferiority criteria for primary endpoint: With respect to the primary study objective, noninferiority of DE-126 to Timolol is established if the upper limit of the two-sided 95% confidence interval for the difference in the mean IOP (DE-126 minus Timolol) is ≤ 1.5 mmHg at all nine timepoints and ≤ 1.0 mmHg in majority (five or more) of the nine timepoints.

Superiority of DE-126 to Timolol for the primary efficacy endpoint will be claimed if the upper limit of the two-sided 95% confidence interval for the difference in the mean IOP (DE-126 minus Timolol) is < 0 mmHg at all nine timepoints.

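### The stated 70% power does not follow from the plan's inputs for the primary success rule; with 4.0 mmHg as the SD entering the model, they give about 51%

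*Protocol*

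**What the plan says.** Protocol 9.3.1, the Statistical Methods part of the Synopsis and SAP 3.3 carry the same calculation: two-sided 5% error, a 1.5 mmHg margin, a true difference of 0, and "SD of 4.0 mmHg and a correlation coefficient of 0.6 among repeated measures". The result is that "approximately 280 adult subjects in total (140 subjects per treatment arm) will provide 70% power to demonstrate non-inferiority". A 5% dropout allowance brings the total to 294. No other margin is named in that text.

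The success rule has two conditions. Protocol 9.3.2 requires the upper limit of the 95% interval to be "≤ 1.5 mmHg at all nine time points and ≤ 1.0 mmHg in majority (5 or more) of the time points". SAP 8.1.1.1 has the same rule: "≤ 1.5 mmHg at all nine timepoints and ≤ 1.0 mmHg in majority (five or more) of the nine timepoints".

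The analysis adjusts for baseline. SAP 6.1 says that in general "baseline IOP score will be adjusted in the inferential analysis of each IOP endpoint", and SAP 8.1.1.1 says "A separate MMRM will be used for IOP at each scheduled timepoint", with baseline IOP as the covariate.

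Neither document says whether 4.0 is a raw or a baseline-adjusted SD, what correlation between baseline and post-baseline IOP was assumed, which pattern across the nine timepoints the 0.6 describes, or which success rule the 70% refers to.

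**The concern.** The sample-size text cites the 1.5 mmHg margin only, while success also needs five of nine limits at or below 1.0 mmHg. With 140 per arm and SD 4.0, that second condition is demanding: at a single timepoint it is met only about 55% of the time when the drugs are equal. It is therefore hard to see how the full rule could reach 70%.

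The 70% is the plan's only statement of how likely the trial is to meet its primary objective if the two drugs are equal. Primary non-inferiority is also the first step of the fixed sequence (Protocol 9.3.3, SAP 6.4), so failing it stops the key secondary test and both superiority tests. Anyone approving the trial, or interpreting a failed result, needs to know whether that chance is near one half or near three quarters.

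**Working it through.** **Inputs.** From Protocol 9.3.1: n = 140 per arm, true difference 0, SD 4.0, correlation 0.6, two-sided 5% (z = 1.96). From Protocol 9.3.2 and SAP 8.1.1.1: the two-part rule. Allocation is 1:1 (Protocol 6.5).

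**One timepoint.** SE = 4.0 × √(2/140) = 0.478, and 1.96 × 0.478 = 0.937.
- Margin 1.5: the observed difference must be at most 1.5 − 0.937 = 0.563. Power = Φ(1.5/0.478 − 1.96) = 88%.
- Margin 1.0: the observed difference must be at most 1.0 − 0.937 = 0.063. Power = Φ(1.0/0.478 − 1.96) = 55%.

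**Full rule, SD 4.0 entering the model, all correlations 0.6.** Write each of the nine estimated differences as 0.478 × (√0.6·Z + √0.4·E), with Z shared and the E independent standard normals. Given Z, let a be the chance that an estimate is at most 0.063, and b the chance that it lies between 0.063 and 0.563. The conditional chance of success is the sum over k = 5 to 9 of C(9,k)·a^k·b^(9−k). Averaging over Z gives:
- all nine limits ≤ 1.5: 61.1%
- at least five limits ≤ 1.0: 56.4%
- both: **51.1%**

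Simulation with t critical values, and simulation of the fitted models without a baseline covariate, give 50.5–50.7%. With all 147 randomized per arm the full rule gives 54.0%. On this reading, 70% would need about 192 evaluable subjects per arm.

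**Other correlation patterns, SD still 4.0.** The full rule gives:
- equal 0.5 / 0.7 / 0.8 / 0.9: 48% / 54% / 55% / 55%
- 0.6 within visit, 0.4 between visits: 47%
- visit-by-clock product (0.6, or 0.36 when both differ): 48%
- 0.8 within visit, 0.6 between; also 0.9 within, 0.6 between: 53%
- AR(1) 0.6 over the nine ordered points: 40–41%

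No equal correlation can help. The five-of-nine condition alone has probability between 63% (correlation near 0) and 55% (near 1), and the full rule cannot exceed it.

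**4.0 as the raw SD, with baseline adjustment.** The model SD is 4.0 × √(1 − r²), where r is the baseline-to-post correlation. The plan gives no value for r, so it is varied here. The low end of each range uses clock-specific baselines with a separate model per clock time and all other correlations 0.6. The high end uses an equal residual correlation of 0.6.

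| r (assumed) | Model SD | Full-rule power |
|---|---|---|
| 0.30 | 3.82 | 55–57% |
| 0.40 | 3.67 | 59–62% |
| 0.50 | 3.46 | 65–68% |
| 0.53 | 3.39 | 68–71% |
| 0.55 | 3.34 | 70–73% |
| 0.60 | 3.20 | 76–77% |

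So 70% corresponds to a model SD of about 3.4, or r of about 0.52 to 0.55.

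**Near-matches.** A 90% interval with 147 per arm gives 68.6%. The mean of three measures tested against 1.0 mmHg gives 68.5%. The five-of-nine condition alone at one-sided 5% gives 70.8%. Each departs from the planned test.

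**The case against.** The best answer is that the planned model adjusts for baseline IOP taken at the same clock times, so baseline is itself a repeated measure. If 4.0 is the raw SD and 0.6 covers baseline as well, power is 76–77% from stated numbers only, and the printed 70% is conservative. This stands as a fair reading. It is why the point is that the figure cannot be derived, and not that the trial is underpowered. But it gives 77%, not 70%.

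A second answer is that the 70% may describe only the 1.5 mmHg condition. All nine limits at or below 1.5 does reach about 71% at an equal correlation of 0.8, or about 70% with a baseline correlation near 0.35. Both need inputs the plan does not give, and both leave out half of the success rule.

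Third, the 40% comes from AR(1), which pushes distant pairs far below 0.6. That is so; it is an illustration of sensitivity and not a bound. With every pair at 0.6 or higher and SD 4.0 in the model, the range is 51–55%. Nor is 77% a ceiling, since a stronger baseline correlation would give more.

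Fourth, if 4.0 is raw, the adjusted analysis gains precision whether or not the sponsor allowed for it, so 51% could understate the true chance. That also stands: 51% is the power on the assumption that 4.0 is the model SD.

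Finally, nothing downstream uses the figure: there is no interim analysis, and the three statements agree with each other. That limits the damage to planning and interpretation. It does not make the figure right.

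**Conclusion.** The concern holds and the text must be corrected. No reading of the stated inputs, with two-sided 5% and 140 per arm, gives 70% for the primary rule. Taking 4.0 as the SD entering the model with equal correlation 0.6, the power is about 51%. Taking 4.0 as raw and 0.6 as the baseline correlation too, it is about 76–77%. Over the readings examined it runs from about 40% to 77%, depending on inputs the plan leaves out.

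These results assume complete data on 140 per arm, normally distributed estimates, the same SD at every timepoint and a true difference of 0 at all nine. The baseline correlations are assumptions, since the documents give none. The treatment estimates, confidence intervals and decision rule are not affected.

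**What to change.** Keep the sample size. In the Synopsis, Protocol 9.3.1 and SAP 3.3, replace the 70% with the simulated power of the complete rule: all nine limits at or below 1.5 mmHg and at least five at or below 1.0 mmHg. Beside it, state:
- whether 4.0 mmHg is the raw or the baseline-adjusted SD;
- the baseline-to-post correlation, if the calculation relies on adjustment;
- the correlation pattern across the nine timepoints to which 0.6 applies.

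If a baseline correlation near 0.53 was in fact assumed, one sentence saying so, together with the rule it refers to, settles the matter. If none was assumed and 4.0 went into the calculation unadjusted with equal correlation 0.6, the figure to print is about 51%, labelled as resting on those assumptions.

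The cost is wording in three places and one short simulation. No patients are added. The printed power may turn out less favourable.
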